7.3.4 Interim analyses

This is a single-arm open label study. The interim analysis may be done after recruitment has been completed. The analyses will include the assessment of safety and efficacy if conducted. The result from the interim analysis may be presented at professional conferences and published in articles after stop of recruitment.

7.4 HANDLING OF MISSING DATA

Missing or incomplete AE dates are imputed according to BI standards.

- For PFS:
 - If a patient is known to have progressed, but the date of progression is not attainable, the last date when the patient was assessed will be used as date of progression.
 - o If a patient's vital status or progression status is unknown at the follow-up visit, the patient will be censored at the last contact date.

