5.1.1 Endpoint(s) of efficacy

Disease Assessment will be based on the assessment of cancer related symptoms and, if available, radiologic assessments as per standard of care at the site.

Data regarding tumour assessments that are performed according to local standard of care for NSCLC may contribute to:

• Time to symptomatic progression (TTSP) is defined as the time from first administration of afatinib (Giotrif®) to the date of first documented clinically significant symptomatic progression that required change in or stopping anti-cancer treatment according to investigator's assessment.

Data regarding tumour assessments that are performed according to local standard of care for NSCLC may contribute to Progression-Free Survival (PFS), defined as time from the date of the first administration of afatinib (Giotrif®) to the date of progression or to the date of death, whichever occurs first.

No specific tumour measurements are required per trial protocol.

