7.3.2 Secondary analyses

Progression-free survival

Progression-free survival is the time from start of treatment to the date of disease progression or death, whichever comes first.

For patients with known date of progression:

Progression-free survival [days] = date of progression (or of death if no earlier progression) – (date of start of treatment) + 1

For patients known not to have progressed, i.e., those remaining on trial drug:

Progression-free survival (censored) [days] = date of last contact showing no disease progression or death - (date of start of treatment) + 1.

Patients with unknown progression status or unknown date of progression will be censored at the last contact date, refer to Section 7.4 for more detail.

Kaplan-Meier estimates and 95% confidence intervals for the 25th, median, and 75th percentiles of the survival distribution will be calculated for progression-free survival,

Proprietary confidential information.

Page 59 of 95

using Greenwood's standard error estimate. Kaplan-Meier curves will be produced without confidence intervals.

Tumour response according to investigator's assessment

Each patient will be assigned to one of the following categories:

- 1. Complete response
- 2. Partial response
- 3. Stable disease
- 4. Progressive disease
- 5. Not evaluable for response, reasons to be specified (e.g. early death, tumour assessments incomplete, etc.)

In the case that the tumour assessment was not based on radiological tumour imaging the categories 'complete response' and 'partial response' will be grouped together. Objective Response (OR) is defined as complete and partial responses according to investigator's assessment.

Time to tumour response is defined as the time from the start of treatment to the date of first recorded CR or PR.

The duration of tumour response is the time from first documented CR or PR to the time of progression or death (or date of censoring for PFS).

Patients whose best assessment is stable disease, partial, or complete response will be considered to have achieved disease control. Duration of disease control will be the same as time to progression, but restricted to patients who achieve disease control.

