6.6 HANDLING OF MISSING DATA AND OUTLIERS

Missing or incomplete AE dates are imputed according to BI standards (see “Handling of missing and incomplete AE dates”).[\(1\)](#)

For efficacy data, the following rules will apply:

- For PFS, duration of objective response and duration of disease control, if a patient is **known** to have progressed during the treatment period, but the date of progression is not attainable, the following sequence for imputation of progression date will be followed:
 - Use the date of cancer-related symptoms assessment or visit date in which the progression was recorded (whichever is earliest).
 - If this is missing, the last known visit date or cancer related symptoms assessment date prior to the recorded progression (regardless of the disease assessment result at that visit) will be used.
 - If any such patient has no visit date or cancer related symptoms assessment date recorded at all, the date of first administration of study medication will be used as the date of disease progression.
- For overall survival, if a patient is known to have died (due to any cause), but date of death is not attainable, the last date when the patient is known to be alive will be used as date of death.

For partial treatment discontinuation date, the following logic is applied:

If month and year are known but day is missing, then use date of death if within the same month for a patient who died. Otherwise use last day of the month.

Missing biomarker values will not be imputed.

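### The protocol's PFS censoring rules make no exception for a known death or a documented progression, and nothing says which rule takes precedence

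*Protocol*

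**What the plan says.** **Definition.** Protocol 5.1.1 runs PFS from first dose "to the date of progression or to the date of death, whichever occurs first". Protocol 7.3.2 agrees: "Progression-free survival is the time from start of treatment to the date of disease progression or death, whichever comes first".

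**Event formula.** The only formula in 7.3.2 that uses a death date takes the "date of progression (or of death if no earlier progression". It stands under a heading for patients whose progression date is known. The next heading covers patients known to be progression-free, whom the protocol equates with those still on trial drug.

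**Censoring rules.** Protocol 7.3.2 adds: "Patients with unknown progression status or unknown date of progression will be censored at the last contact date". Protocol 7.4 says that if a patient's "vital status or progression status is unknown at the follow-up visit, the patient will be censored at the last contact date".

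**Undated progression.** Protocol 7.4 treats this as an event: "If a patient is known to have progressed, but the date of progression is not attainable, the last date when the patient was assessed" supplies the event date. SAP 6.6 also gives an imputed event date to patients known "to have progressed during the treatment period, but the date of progression is not attainable, the following sequence for imputation of progression date".

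**SAP.** Section 4 of the SAP moves the efficacy endpoints to Section 5.3, Further Endpoints, which is redacted in the public copy. In the visible text, SAP 6.6 has a death-date rule for overall survival. It has none for death as a PFS event, and no censoring rule for status unknown at follow-up.

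**The concern.** The definition makes death an event, but the operational rules do not clearly carry that through. A patient who stops afatinib for toxicity and then dies with unknown progression status fits neither heading in 7.3.2: there is no progression date, and the patient is not still on drug. The patient does fit the censoring sentence that follows. Under 7.4 a known death gives no protection, because the rule applies when either vital status or progression status is unknown.

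The 7.4 rule also depends on progression status at a visit that is not designed to establish it. The flow chart schedules disease assessment at the treatment visits and at end of treatment, but not at follow-up. The follow-up contact may be a phone call, and Table 6.2.4: 1 lists adverse events, new anti-cancer medication, date of death and patient status for the eCRF, with no disease assessment.

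Two programmers could therefore follow the protocol and obtain different event counts. Censoring a patient at about the time of a known event is informative and moves the Kaplan-Meier curve upward. With a single arm, no comparator shares the bias. Efficacy is a stated objective (Protocol 2.2), and Protocol 7.3.4 allows interim efficacy results to be published.

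**Working it through.** The documents give no planned PFS event count, median or precision, so there is no figure to reproduce. The check has two parts.

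**1. The rules applied to three kinds of patient**

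| Patient | Points to event | Points to censoring |
|---|---|---|
| Died, progression status unknown | PFS definition (5.1.1, 7.3.2); death clause in the event formula | 7.3.2 unknown-status sentence; 7.4 follow-up rule |
| Dated progression, then lost before the follow-up call | PFS definition; event formula, directly | 7.4 follow-up rule only |
| Known progression, no date | 7.4 first bullet; SAP 6.6 | 7.3.2 unknown-date clause |

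The first row is the real problem: two censoring rules apply, and the formula that would make the death an event sits under a heading the patient does not fit. The second row is weaker, because the patient falls squarely under the event formula. The third row is a separate issue. It is shown because there 7.3.2 and 7.4 give opposite answers, which confirms that the two sections were not written as one ordered set of rules.

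**2. Direction and size if events are censored**

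Inputs:
- True median PFS (assumed for this trial): 11.1 months, from the afatinib arm of the earlier first-line phase III trial 1200.32. The range is 8 months (pre-treated patients in phase II trial 1200.22, independent review) to 13.6 months (common mutations in 1200.32). All are in Protocol 2.3.
- q, the share of true PFS events recorded as censored: not in the documents; taken as 2%, 5% and 10%.

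Formula: with exponential times and hazard λ, relabelling a random share q of events leaves an apparent hazard of λ(1-q). The apparent median is then ln 2 / [λ(1-q)] = true median/(1-q).

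For 11.1 months: 11.1/0.98 = 11.33; 11.1/0.95 = 11.68; 11.1/0.90 = 12.33.

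A simulation checked this, using 481 patients, exponential PFS, administrative censoring uniform over 24 to 48 months, and 1,000 runs. Affected deaths were censored 0-28 days before the event and affected progressors 0-14 days after it. Each cell gives the formula, then the two simulated means.

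| True median (months) | q = 2% | q = 5% | q = 10% |
|---|---|---|---|
| 8.0 | 8.16 (8.16, 8.17) | 8.42 (8.44, 8.46) | 8.89 (8.86, 8.91) |
| 11.1 | 11.33 (11.35, 11.36) | 11.68 (11.68, 11.71) | 12.33 (12.33, 12.38) |
| 13.6 | 13.88 (13.94, 13.95) | 14.32 (14.34, 14.37) | 15.11 (15.10, 15.15) |

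With q = 0, when known events are always counted, the simulation returns 8.01, 11.11 and 13.63, so the method itself adds almost nothing.

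For scale, even if all 481 patients had a PFS event, q = 2%, 5% and 10% would mean 0.02 × 481 ≈ 10, 0.05 × 481 ≈ 24 and 0.10 × 481 ≈ 48 patients.

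**The case against.** The best defence is that the sponsor's intent is clear. The death clause in the event formula has work to do only for patients who died without a recorded progression, so reading the heading strictly empties the clause. Disease is assessed every 28 days and at end of treatment, and date of death is actively sought, so a death with truly unknown progression status should be uncommon. Section 7.4 concerns missing data, and a dated progression is not missing. Its first bullet and SAP 6.6 count even undated progressors as events, so censoring dated ones would make little sense. The unseen SAP section may also settle the order.

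Most of this stands. It makes the progressor reading unlikely and rules out any claim that events will be censored. It does not remove the conflict for deaths, because intent has to be inferred against two explicit sentences that contain no exception.

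A reader might go further and infer that the reported PFS is overstated by a known amount. One route is to take the on-treatment adverse-event deaths in the earlier phase III trials (5.7% and 5.9%, Protocol 2.3) as the affected share. The documents do not support that. Those figures count all such deaths, not deaths with unknown progression status, and patients on treatment are the ones assessed regularly. Nor do the documents give any rate of progressors lost before follow-up.

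**Conclusion.** The point holds as a conflict of rules without precedence. It is firm for patients known to have died with unknown progression status and weak for documented progressors lost before follow-up. If such events are censored, the bias is upward. On an assumed true median of 11.1 months and roughly exponential times, it is about 0.2-0.3 months at q = 2%, 0.6 months at q = 5% and 1.2-1.3 months at q = 10%. The actual q is not given and may be small enough not to matter.

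The redacted SAP section could already contain the right rule. No test or error rate is affected: Protocol 7.2 plans no confirmatory testing, the primary endpoint is adverse events, and the SAP classes efficacy as further endpoints.

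The disease-control wording is a minor consistency point only. "Duration of disease control will be the same as time to progression, but restricted to patients who achieve disease control" relies on a term that is not defined, whereas duration of response expressly counts death. It is not evidence of bias in PFS.

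**What to change.** State one order in Protocol 7.3.2 and 7.4, and confirm that the SAP's PFS rule matches it:

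- (a) A documented progression is an event, whatever is known at follow-up.
- (b) Otherwise, a known death is an event at the date of death, whatever the progression status.
- (c) Only patients with neither are censored.

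The heading over the event formula in 7.3.2 should be widened to include patients who died without a recorded progression. In the disease-control sentence, define time to progression and say whether death counts.

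The cost is a few sentences and no new data collection. If the literal rules would otherwise have been programmed, the reported PFS may come out slightly shorter.

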3. DESCRIPTION OF DESIGN AND TRIAL POPULATION

This trial will evaluate the safety, tolerability and efficacy of the investigational drug afatinib (Giotrif®) in patients with locally advanced or metastatic non-small cell lung cancer (NSCLC) harboring EGFR mutation(s) and have never been treated with an EGFR-TKI. EGFR mutation positivity of all patients needs to be established and documented prior to enrolment into the trial. Treated patients will visit the investigator at regular intervals as specified in the Flow chart.

All entered patients (i.e., patients that have been treated with the trial medication) will receive continuous treatment of afatinib (Giotrif®) in the absence of disease progression or meeting any other trial withdrawal criteria (see Section 3.3.4). The trial is considered concluded when all patients have discontinued trial medication and/or have access to Afatinib via options included but not limited to an alternative clinical trial, marketed product, an expanded-access program, named patient use program, compassionate use protocol or other means based on local regulation and completed the follow up or are lost to follow up.

Enrolment of new patients into the trial will end once enrolment goal in the trial has been met and/or if any of the criteria in Section 3.3.4.2 are met.

All patients will visit the investigator at regular intervals for assessment of safety as outlined in the Flow chart. Disease Assessment will be performed at each visit (i.e., every 28 days) until disease progression or withdrawal for another reason. Disease Assessment will be based on the assessment of cancer related symptoms and, if available, radiologic assessments as per standard of care (SOC) at the site. The investigator is not obligated to perform any radiologic scans as part of this trial. However, if such scans were performed as part of standard of care this information should be recorded on the Disease Assessment case report form.

Participation will be open to physicians experienced in treating patients with NSCLC and who can complete the site qualification and initiation process.

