The sponsor may remove patients from the study if the patient has access to afatinib via options included but not limited to an alternative clinical trial, marketed product, an expanded-access program, named patient use program, compassionate use protocol or other means based on local regulation. This may mean a change in packaging and labelling. The cost of any ongoing supply of study medication will be incurred by the sponsor until progression occurs. If a patient is removed from the study treatment, an end of treatment 0-14 days later and a follow up visit 28 days later will be performed to ensure all adverse events are followed up and then the patient will be considered to have completed the trial.

When discontinuation is due to a SAE the investigator must follow the event until it is resolved, becomes chronic, or remains stable with no resolution expected. Data on these events must be collected in the electronic case report form (eCRF). For guidelines in the management of class expected adverse events, refer to Appendix 10.1.

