6.2.4 Follow-Up

The Follow-up (FU) visit should occur 28 (-7) days after the EOT visit.

Follow-up visits should be scheduled for patients who met the trial withdrawal criteria (see Section 3.3.4). This visit marks the end of the patient's participation in the trial. Patients will not be required to attend the clinic for this visit. The clinic staff will contact the patients or their caregivers by telephone and inquire about any adverse events that might have occurred since the last visit and if applicable follow up on any unforeseen pregnancy during the trial. All concomitant medication should be added to the patient's chart. The Patient Status eCRF will be completed at this time.

Any additional (unscheduled) follow-up visits should be scheduled for patients with unresolved SAEs, AEs, or laboratory abnormalities who have discontinued trial participation. These events must be followed until resolution or until agreement is reached between the local medical monitor and the investigator that further follow-up is no longer required.

Doc. No.: U13-1326-02 Trial Protocol Page 57 of 95

Table 6.2.4: 1 Follow-up (FU) Visit/EOT + 28 Days (-7)

	What to Include in the Patient's Chart	What to include in eCRF
Adverse events	Patients should be asked to report any hospitalizations, emergency treatments, or new medications as well as any general health issues that may have surfaced since their last visit. All the information collected should be recorded in the patient's chart. Refer to Sections: 5.2.2 and 5.2.2.2 for protocol specific requirements regarding the collection and reporting of adverse event information.	All relevant AEs and all SAEs.
Concomitant Medications	Patients should be asked to report any concomitant drug use (including, but not limited to,: non-prescription medications, anaesthetic agents, homeopathic/herbal remedies and dietary supplement preparations).	No concomitant medications will be recorded on eCRFs.
Patient Status	Document any information regarding the patient's status during the planned observation time (i.e., 28 days after the patient's last dose of medication).	Any new anti-cancer medication that the patient has taken since EOT visit.
	When applicable, every effort should be taken to collect and document information on date of death.	Date when the patient completed the planned observation time.
	Note: any AE which results in death is considered an SAE.	Date of death Patient's status

Page 58 of 95

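### PFS for patients of unknown progression status is censored at last contact, which can be a follow-up call with no disease assessment; the upward bias is small, about 1–8 days on the median

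*Protocol*

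**What the plan says.** **Censoring rules.** Protocol 7.3.2 has two. The first is headed "For patients known not to have progressed, i.e., those remaining on trial drug" and censors at the "date of last contact showing no disease progression or death". The second covers everyone else without a usable status: "Patients with unknown progression status or unknown date of progression will be censored at the last contact date". Section 7.4 restates the second rule: if vital or "progression status is unknown at the follow-up visit, the patient will be censored at the last contact date". Last contact date is not defined.

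**When disease is assessed.** Protocol Section 3: "Disease Assessment will be performed at each visit (i.e., every 28 days) until disease progression or withdrawal for another reason". The Flow Chart marks Disease Assessment at Visit 2 onwards and at EOT, but not at follow-up. EOT falls 0–14 days after the last dose (6.1.3).

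**What happens after EOT.** The follow-up contact is due 28 (-7) days after EOT (6.1.4); SAP 6.7 gives the window as 21 to 28 days. Section 6.2.4: "The clinic staff will contact the patients or their caregivers by telephone and inquire about any adverse events". Table 6.2.4:1 also lists patient status, date of death and new anti-cancer medication. Patients with unresolved events may be contacted later still: "These events must be followed until resolution or until agreement is reached" (6.2.4), and "When discontinuation is due to a SAE the investigator must follow the event until it is resolved" (3.3.4.1).

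**SAP.** Section 4 reclassifies the efficacy endpoints as further endpoints. Visible Section 6.6 imputes missing progression and death dates but gives no censoring rule for unknown status. The further-endpoint sections are redacted.

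**The concern.** The stricter standard, a contact that shows no progression, is reserved for patients still on drug. Someone who stops for toxicity, withdraws, or is moved by the sponsor to another afatinib supply appears to fall under the looser rule. If that person's progression status is not established at the follow-up contact, PFS is still counted as event-free up to it.

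Over that interval deaths are collected, but no disease assessment is scheduled. The patient stays in the risk set while a progression could go unrecorded, so the estimated hazard is too low and PFS too long. The patient may also have started another anti-cancer drug by then, which the follow-up form records but the visible PFS rules do not address. Duration of response uses the PFS censoring date (7.3.2), so it carries the same error. Section 7.3.4 allows interim efficacy results to be published.

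**Working it through.** The plan gives no expected PFS, event count or sample-size calculation (7.6), so there is no stated figure to reproduce.

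**Step 1: the unassessed interval.**
- EOT includes a Disease Assessment, so on schedule the gap runs from EOT to follow-up: 21–28 days.
- Time from last dose to follow-up is longer: 0 + 21 = 21 days up to 14 + 28 = 42 days. The part before EOT is covered by the EOT assessment.
- If the patient is lost before follow-up, last contact may be EOT or an earlier assessed visit, and nothing is over-credited.
- The gap is longer only if EOT is missed, or if a later adverse-event call counts as last contact. The text does not exclude the latter.

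**Step 2: effect on the Kaplan–Meier curve.** Assumptions, none of them planning values of this trial:
- exponential PFS, scaled to the 11.1-month afatinib median that Protocol 2.3 cites from its first-line Phase III trial: 11.1 × 30.4375 = 337.9 days, so λ = 0.6931/337.9 = 0.00205 per day;
- a share f of patients (5–30%) who stop without progression, independently of prognosis;
- a gap of g days in which no event is recorded.

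With total exit rate Λ = λ/(1 − f), patients wrongly still at risk at any time are about f(e^{Λg} − 1) per patient truly at risk. The estimated hazard shrinks, and the median grows, by the factor 1 + f(e^{Λg} − 1).
- f = 0.05, g = 21: 0.05 × (e^{0.0454} − 1) = 0.0023; × 337.9 = 0.8 day.
- f = 0.20, g = 28: 0.20 × (e^{0.0718} − 1) = 0.0149; × 337.9 = 5.0 days.
- f = 0.30, g = 28: 0.30 × (e^{0.0821} − 1) = 0.0257; × 337.9 = 8.7 days.

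Simulation (481 patients, 400 runs per scenario, same assumptions) agrees. Rise in days for gaps of 21 and 28 days:

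| Share affected | Median | 75th percentile of PFS |
|---|---|---|
| 5% | 0.8, 1.0 | 1.6, 1.9 |
| 10% | 1.5, 2.2 | 3.1, 4.6 |
| 20% | 3.5, 4.9 | 7.8, 9.8 |
| 30% | 6.4, 8.4 | 13.6, 17.1 |

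The upper percentile moves about twice as far because, under an exponential, it lies at twice the median. Assumed medians of 8 or 13.6 months give nearly the same shifts (8.3 days at 30% and 28 days in both). A 42-day gap at 30% gives 11.9 days. Recording a fifth of post-stop events as deaths, with a post-stop hazard of one to two times (and a median of 11.0 months), gives 2–3 days at 14% affected and 4–5 days at 25%, for a 28-day gap.

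**Step 3: scale.** Without censoring, the approximate 95% half-width for the median is 1.96 × (11.1/0.693)/√481 = 1.4 months, about 44 days. The shift is well inside this.

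**Step 4: a related conflict.** For a patient known to have progressed but with no date, 7.3.2 censors at last contact. Section 7.4 instead counts an event at the last date assessed. SAP 6.6 also counts an event, for progression during the treatment period, through a sequence of visit and symptom-assessment dates. The same patient can be censored or an event depending on the section followed.

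**The case against.** The strongest counter-argument is the redaction. SAP Section 4 sends PFS to a further-endpoint section that cannot be read, and visible 6.6 shows the SAP refining the protocol's other missing-data rule for PFS. It may have refined this one too, so the visible SAP's silence proves nothing. This stands and limits confidence; the protocol wording would still need alignment.

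Materiality is also low: PFS is descriptive, in a single-arm trial with no hypothesis test and no required tumour measurements. This stands.

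Four stronger readings are tempting, and the documents do not support them.
- **That 7.3.2 and 7.4 disagree on unknown status.** They state the same rule. The contrast lies inside 7.3.2, between patients on drug and the rest.
- **That progression cannot be learned at follow-up.** The contact covers general condition, patient status and new anti-cancer medication, and disease assessment in this trial rests largely on symptoms. The call can be informative. The accurate statement is that no disease assessment is listed there and the censoring rule does not require one.
- **That every stopper gains up to 42 unassessed days.** This overlooks the EOT assessment.
- **That the median is inflated by 0.4–1.0 month.** This needs a 180-day gap for every patient who stops (14–25% of the total). The documents give no such gap; extended follow-up applies only to unresolved events. Section 7.4 speaks of status at the follow-up visit, which 6.2.4 makes the end of participation.

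**Conclusion.** The rule as written is wrong in a known direction, and its effect is small. On schedule it can credit about 21–28 unassessed days to a patient who stops without progression and whose status is unknown at follow-up. This adds about 1–8 days to the median and roughly 2–17 days to the 75th percentile of PFS, with duration of response affected through the shared censoring date. These figures rest on exponential PFS with a median of about 11 months, 5–30% of patients affected, and stopping unrelated to prognosis. Informative stopping is a separate matter that this check does not cover. Priority is minor. Confidence is moderate because the SAP's further-endpoint text is not visible.

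**What to change.** In Protocol 7.3.2 and 7.4, and in the SAP unless its redacted section already does so, censor every patient without documented progression or death at the date of the last Disease Assessment showing no progression, or at the date of first dose if there is none. Drop last contact as a PFS censoring date.

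In the same edit, choose one treatment for a known progression with no date and state it identically in 7.3.2, 7.4 and SAP 6.6. Two of those three places already count it as an event.

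The cost is wording and the corresponding programming. No new data are needed, because the Disease Assessment is already on the case report form. PFS may come out slightly shorter.

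A progression question on the follow-up form would be a separate change of little use now: Amendment 2 (2017) already recorded 481 as the actual number entered, and a new item cannot recover status for patients whose follow-up contact is past.
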